## **6.3 EXCLUSIONS TO ROUTINE DATA COLLECTION:**

### **6.3.1 Adverse Events**

The following Adverse Events will be captured only in the source documents and will not be reported in C3D

- Laboratory values that do not support the diagnosis of a reportable event
- All grade 1 events, except for bleeding events, which will all be captured regardless of grade.
- Grade 2 events that are not related to the treatment
- Grade 1, 2, and 3 lab values drawn outside of the protocol specified time points that are not assessed as clinically significant by the PI or his designee and are not associated with an adverse event
- Events related to vascular access devices (occlusion, thrombi, hospitalizations for insertion or removal)

**Note:** Events that result in a hospitalization for convenience will not be reported.

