### **3.2 DRUG ADMINISTRATION**

Given our recent findings pertaining to ABCB4, ABCB11, RALBP and CYP8B1 SNPs that distinguish patients who did and did not experience mithramycin-mediated hepatotoxicity on this trial, the protocol has been amended to accrue only those patients with favorable ABCB4/ABCB11/RALBP/CYP8B1 genotypes. Fourteen of these patients (7 with primary thoracic malignancies and 7 with extrathoracic malignancies metastatic to the chest) will receive mithramycin infusions during cycle 1 at 30mcg/kg per day. Those patients tolerating 30 mcg/kg infusions during the first cycle will receive subsequent cycles of mithramycin at a dose of 50 mcg/kg using the same infusion schedule. Based on the PK data obtained on this trial to date, this dose of mithramycin would be expected to produce Cmax of ~40nM and steady state levels of ~20-25nM, concentrations approximating lowest therapeutic doses in preclinical tissue culture experiments. Patients exhibiting dose-limiting toxicities during cycle 1 will receive subsequent infusions at a dose of 25mcg/kg, with dose reduction guidelines listed in section 3.3. If one or more patients in each cohort exhibit response to therapy, an additional 14 patients will be accrued to the respective cohort(s) to further define response rates Simon Second Stage). Drug administration in the Second Stage will be identical to that in the First stage.

Mithramycin will be administered intravenously via central line over 6 hours once daily for 7 days to be repeated every 21 days (+7 days/-3 days). Three cycles will constitute one course. Intravenous hydration will be provided as clinically indicated.

**Note:** At least 23 hours should elapse between the beginning of one infusion and the beginning of the next.

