#### **7.2.2 NCI-IRB Requirements for PI Reporting Continuing Review**

The protocol PI will report to the NCI-IRB:

1. A summary of all protocol deviations in a tabular format to include the date the deviation occurred, a brief description of the deviation and any corrective action.
2. A summary of any instances of non-compliance
3. A tabular summary of the following adverse events:
  - All Grade 2 **unexpected** events that are possibly, probably or definitely related to the research;
  - All Grade 3 and 4 events that are possibly, probably or definitely related to the research;
  - All Grade 5 events regardless of attribution;
  - All Serious Events regardless of attribution.

**NOTE:** Grade 1 events are not required to be reported.

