## **7.3 IND SPONSOR REPORTING CRITERIA**

### **7.3.1 Expedited Adverse Event Reporting Criteria to the IND Sponsor**

During the first 30 days after the subject receives investigational agent/intervention, the investigator must immediately report to the sponsor, using the mandatory MedWatch form 3500a or equivalent, any serious adverse event, whether or not considered drug related, including those listed in the protocol or investigator brochure and must include an assessment of whether there is a reasonable possibility that the drug caused the event. For serious adverse events that occur more than 30 days after the last administration of investigational agent/intervention, only report those that have an attribution of at least possibly related to the agent/intervention.

Required timing for reporting per the above guideline:

- Deaths (except death due to progressive disease) must be reported via email within 24 hours. A complete report must be submitted within one business day.
- Other serious adverse events as well as deaths due to progressive disease must be reported within one business day

Events will be submitted to the Center for Cancer Research (CCR) at: [[contact]](mailto:[contact]) and to the CCR PI and study coordinator.

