### **11.1.5 Administration procedures**

Infuse intravenously over 6 hours using chemotherapy precautions. Infusion bags have to be protected from light from the time of preparation through completion of the infusion. Observe frequently for signs of extravasation. Should extravasation occur, the infusion should be terminated at that site and reinstated at another site. Moderate heat should be applied to the site of extravasation to disperse the drug and minimize local tissue irritation and discomfort.

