### **11.1.6 Contraindications**

The following medications are contraindicated:

- Anticoagulants, coumadin- or indandione-derivatives

**Abbreviated Title:** *Mithramycin for Cancer Stem Cells*

**Version Date:** 09/14/2018

- Heparin other than heparin flushes
- Thrombolytic agents
- Aspirin or salicylate-containing products, which may increase risk of hemorrhage
- Dextran
- Dipyridamole
- Sulfinpyrazone
- Valproic acid
- Clopidogrel

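### Section 6.3.1 keeps access-device events, including thrombi, out of C3D with no exception for serious or grade 3 or higher events, so line thromboses can drop out of the reported toxicity incidence

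*Combined protocol and SAP*

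**What the plan says.** Section 6.3.1 opens its list of exclusions with this rule: "The following Adverse Events will be captured only in the source documents and will not be reported in C3D". One bullet reads "Events related to vascular access devices (occlusion, thrombi, hospitalizations for insertion or removal", and the closing bracket ends it. The other bullets are limited by grade, relatedness or clinical relevance; this one is not. The only type of event that the list protects is bleeding: "All grade 1 events, except for bleeding events, which will all be captured regardless of grade".

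On route, section 3.2 states: "Mithramycin will be administered intravenously via central line over 6 hours once daily for 7 days". Section 6.1 makes C3D the database for all clinical data. Section 6.2 sends adverse events there, subject to the 6.3.1 exclusions.

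On reporting, section 7.3.1 requires the investigator to send the sponsor "any serious adverse event, whether or not considered drug related" in the first 30 days after drug; after that, serious events at least possibly related to it are sent. Section 7.2.2 puts "All Serious Events regardless of attribution" in the continuing-review table for the IRB. Section 7.1.5 counts inpatient hospitalization as serious. None of the three exempts access-device events.

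Toxicity is a secondary objective (1.1.2). Section 8.1 plans tables of incidence by type and severity and does not say which data they draw on.

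**The concern.** Every patient must have a central line. By section 3.2, a course is 3 cycles of 7 daily six-hour infusions, so 3 × 7 = 21 infusions through that line. A thrombus on the line is a foreseeable event in this trial. Under 6.3.1 a serious or grade 4 thrombus is handled in the same way as a briefly blocked lumen: neither enters the database.

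Two things are at stake. If the 8.1 tables are built from C3D, which is the natural reading when no other source is named, the incidence of thrombosis can be understated. And the database and the serious-event file will disagree for any serious line thrombosis, with no rule for reconciling them. This matters more than usual here because section 1.3.3 raises disturbed coagulation pathways as one explanation for the drug's historical bleeding, so clotting events belong in the description of its safety.

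**Working it through.** **Side-by-side reading.** The plan states no figure on this point, so there is none to reproduce. Take one case, a serious thrombus on the central line within 30 days of dosing.

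- Source documents: recorded (6.2).
- Sponsor: reported, whatever the attribution (7.3.1).
- IRB continuing-review table: listed, whatever the attribution (7.2.2).
- C3D: not entered, because thrombi are named in the excluded bullet (6.3.1).
- Concomitant-medication data in C3D: section 6.3.2 also leaves out drugs given to treat adverse events, so treatment of the thrombus would not reveal it.
- Toxicity tables (8.1): source not stated. If it is C3D, the event is absent.

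An investigator can obey all of these rules at once. The result is an event that appears in the safety reports and is absent from the clinical database.

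**Scale, with assumed rates.** The documents give no rate for central-line events. Appendix 1 records phlebitis in 11% of patients in a hypercalcemia trial and thrombophlebitis in 3 of 32 in a trial in advanced malignancy. The access route is not given for either, so neither is used as an input. The per-patient rate p of an event kept out of C3D is assumed to be 2%, 5% or 10%.

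Sample sizes come from section 8. If both cohorts stop at the first stage, 2 × 7 = 14 patients. If both go to completion, 2 × 21 = 42. The plan gives a 70% chance of early stopping per cohort at a 5% response rate, so both stop with probability about 0.70 × 0.70 = 0.49. The smaller figure is therefore a realistic outcome if the drug is inactive.

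Expected number omitted = n × p. Chance of at least one = 1 − (1 − p)^n, treating patients as independent.

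| Assumed p | Expected, n = 14 | At least one, n = 14 | Expected, n = 42 | At least one, n = 42 |
|---|---|---|---|---|
| 2% | 0.28 | 1 − 0.98^14 = 25% | 0.84 | 1 − 0.98^42 = 57% |
| 5% | 0.70 | 1 − 0.95^14 = 51% | 2.1 | 1 − 0.95^42 = 88% |
| 10% | 1.4 | 1 − 0.90^14 = 77% | 4.2 | 1 − 0.90^42 = 99% |

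A table showing 0 of 42 would carry an exact two-sided 95% upper limit of 1 − 0.025^(1/42) = 8.4%. That limit would mean nothing if the events had been excluded from the count.

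**The case against.** The strongest reply is that 6.3.1 governs routine database entry only. Serious events still reach the sponsor and the IRB, and nothing prevents the 8.1 tables from drawing on those reports. The secondary objective concerns toxicities of mithramycin, and in a single-arm trial catheter events are hard to separate from drug effects. Keeping them out of drug-toxicity tables could then be a deliberate choice.

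Much of this stands. Oversight is intact, and section 8.1 does not say that its tables come from C3D alone. A reader might infer that serious toxicity is certain to be missing from the tables; the text supports only that it can be. The attribution argument may justify reporting device events apart from drug toxicities. It does not justify leaving serious thrombi out of the database, and a separate row answers it.

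Other stronger readings also lack support:

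- **That every device event is excluded.** The bracket names occlusion, thrombi and hospitalizations for insertion or removal. Whether these are examples or a complete list is not stated, and admission to treat a thrombus is not named.
- **That bleeding at the line is excluded.** Bleeding is not in the bracket, and the same list captures it at every grade. What is missing is a statement of which rule prevails when both could apply.
- **That extravasation is excluded.** It is not named either, and section 11.1.5 treats it as part of giving the drug ("Observe frequently for signs of extravasation").
- **That a line thrombus ends treatment with no recorded cause.** Section 11.1.6 lists "Heparin other than heparin flushes" as contraindicated, but no section says that a thrombus stops mithramycin. Section 3.6.3 requires a status form when a patient comes off therapy.

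**Conclusion.** The point holds in a limited form. Section 6.3.1 excludes access-device events, expressly including thrombi, from C3D whatever their grade or seriousness, although the protocol requires a central line and makes serious events reportable elsewhere. Serious line thromboses can therefore drop out of the reported toxicity incidence, and C3D will not match the serious-event file when one occurs.

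The effect is on a secondary objective. Objective response, the two-stage rule and the sample size do not depend on it. The percentages above rest on assumed rates and on independence between patients, and they count omissions only if the 8.1 tables rely on C3D. They show that an omission is plausible even with 14 patients; they do not estimate how often it will happen. The change is cheap and should be made.

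**What to change.** Amend section 6.3.1 in three places and section 8.1 in one.

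1. Limit the device bullet to non-serious grade 1-2 events and elective admissions for insertion or removal.
2. Require entry in C3D of any access-device event that is serious, grade 3 or higher, or the recorded cause of a held or stopped infusion.
3. State that the existing bleeding-capture rule takes precedence over the device bullet.
4. In section 8.1, report these events as a separate row of the toxicity tables, and name C3D as the source of those tables.

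The events are already in source documents and, when serious, already reported, so the cost is a few sentences and a few extra database entries. Some entries will be unrelated to the drug; the separate row keeps them from being read as drug toxicity.

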### **6.3.2 Concomitant medications/measures:**

- All concomitant medications and measures will be captured in the source documents. Only those medications that the patient is taking at baseline on a routine basis or medications

that cause an AE will be captured in C3D (e.g., onetime medications, PRN medications, supportive medications, electrolyte replacement and medications given to treat adverse events will not be captured in C3D).

## **6.4 DATA SHARING PLANS**

### **6.4.1 Human Data Sharing Plan**

I will share coded, linked human data generated in this research for future research

- in a NIH-funded or approved public repository [clinicaltrials.gov](http://clinicaltrials.gov)
- in BTRIS
- in publication and/or public presentations

at the time of publication or shortly thereafter

### **6.4.2 Genomic Data Sharing Plan**

The study is not subject to the NIH genomic data sharing policy. The gene and microRNA as well as DNA methylation studies performed under this protocol are not genome wide.

## **6.5 RESPONSE CRITERIA**

Objective response and progression will be evaluated in this study using the new international criteria proposed by the Response Evaluation Criteria in Solid Tumors (RECIST) Committee [version 1.1 ]. Note: Lesions are either measurable or non-measurable using the criteria provided below. The term “evaluable” in reference to measurability will not be used because it does not provide additional meaning or accuracy.

### **6.5.1 Response Criteria for Radiographic Studies**

#### **6.5.1.1 Measuring of Soft Tissue Disease**

Response and progression will be evaluated in this study using the new international criteria proposed by the revised Response Evaluation Criteria in Solid Tumors (RECIST) guideline [version 1.1 ]. Changes in the largest diameter (unidimensional measurement) of the tumor lesions and the shortest diameter in the case of malignant lymph nodes are used in the RECIST criteria.

#### **a. Evaluation of Target Lesions**

##### **Complete Response (CR)**

Disappearance of all target lesions. Any pathological lymph nodes (whether target or non-target) must have reduction in short axis to <10 mm

##### **Partial Response (PR)**

At least a 30% decrease in the sum of the diameters of target lesions, taking as reference the baseline sum diameters

##### **Progressive Disease (PD)**

At least a 20% increase in the sum of the diameters of target lesions, taking as reference the smallest sum on study (this includes the baseline sum if that is the smallest on study). In addition to the relative increase of 20%, the sum must also demonstrate an absolute increase

of at least 5 mm. (Note: the appearance of one or more new lesions is also considered progressions)

Note: determination of PD will not be made prior to the Day 60 evaluation.

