## **3 STUDY IMPLEMENTATION**

### **3.1 STUDY DESIGN**

This study will be conducted as a single site, phase II trial utilizing a Simon Optimal Design. Patients will be analyzed in two cohorts on the basis of primary thoracic malignancy vs. extra-thoracic malignancy metastatic to lungs, pleura or mediastinum. The goal of the study is to determine response rates, pharmacokinetics and molecular responses following 6h mithramycin infusions as a prelude to combinatorial studies as well as protocols utilizing 24h continuous infusions targeting pharmacodynamic endpoints in tumor tissues.

Patients will undergo eligibility evaluation in the Thoracic Surgery Clinic (OP-3). Patients deemed eligible for therapy will sign an informed consent and receive mithramycin as described in Section 3.2. Patients may continue to receive mithramycin as long as they tolerate drug and do not have progressive disease (Section 6.4).

Patients on study will be closely monitored for the development of toxicities using regular physical examinations, blood pressure monitoring, and laboratory evaluations with particular attention to the development of any signs of bleeding. Patients will be admitted to the hospital for the first treatment cycle to allow for close monitoring of toxicities. For subsequent cycles, local patients may receive infusions in the day hospital; patients traveling from out-of-town will be admitted to the hospital. Two weeks (plus 12 or minus 3 days) following each course of therapy (three 21-day cycles) patients will undergo appropriate staging studies to determine response to therapy using RECIST criteria.

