### 3.4 CRITERIA FOR ADDITIONAL TREATMENT

Patients will be eligible to continue to receive mithramycin for as long as they do not experience clinical or radiographic disease progression (See section 6.4) and tolerate mithramycin (as defined in Section 3.3).

Patients may receive the next course of mithramycin at the same dose level (or reduced level as above) provided the following criteria are met by day 21.

- patient has stable or responding disease;
- has a platelet count  $\geq 75,000/\mu\text{L}$  (transfusion independent), and an ANC  $\geq 1000/\mu\text{L}$ , and meets other laboratory parameters defined in the eligibility section; and
- has not met any criteria for removal from treatment or off study (Section 3.6)

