### **3.5.4 Follow-up Evaluations:**

After completion the last treatment cycle (See section [3.4](#) for criteria for retreatment), patients will be monitored weekly until all clinically significant toxicities resolve to less than or equal to grade 1 or baseline as follows:

- Toxicity Evaluation
- Laboratory evaluation: CBC, Chem20 equivalent including ionized calcium\*, PT/PTT
- For patients with stable disease or responding to therapy, the following will be done every 2 months until off study criteria are met:
  - History and physical exam
  - Laboratory evaluation: CBC, Chem20 equivalent including ionized calcium\*, PT/PTT
  - Tumor Measurements: CT scan of the chest, abdomen and pelvis as well as PET/CT and brain MR or CT scan.

Note: The patient may have evaluations and lab work obtained through his or her local physician during follow up.

\* Ionized calcium is not part of a standard lab panel and could be omitted if not available or not covered by insurance when performed outside NIH.

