#### **6.5.6 Target Lesions**

All measurable lesions up to a maximum of 2 lesions per organ and 5 lesions in total, representative of all involved organs, should be identified as **target lesions** and recorded and measured at baseline. Target lesions should be selected on the basis of their size (lesions with the longest diameter), be representative of all involved organs, but in addition should be those that lend themselves to reproducible repeated measurements. It may be the case that, on occasion, the largest lesion does not lend itself to reproducible measurement in which circumstance the next largest lesion which can be measured reproducibly should be selected. A sum of the diameters (longest for non-nodal lesions, short axis for nodal lesions) for all target lesions will be calculated and reported as the baseline sum diameters. If lymph nodes are to be included in the sum, then only the short axis is added into the sum. The baseline sum diameters will be used as reference to further characterize any objective tumor regression in the measurable dimension of the disease.

Progressive disease by RECIST criteria [1] noted after the first re-staging scan may represent disease that was not detected on the pre-study scan, and a confirmatory scan will be required at the next scheduled re-staging evaluation unless clinically not indicated. If confirmed, progression should be dated by the initial time when the lesions are first detected. If progressive disease by RECIST criteria is seen after cycle 2, but not confirmed on subsequent restaging scan, the scans from after cycle 2 would serve as the baseline scan to evaluate for disease progression .

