## 8.1 METHODS OF ANALYSIS

Patients who are considered evaluable for response will be included in an analysis of time to progression. Time to progression will be estimated using the product-limit method of Kaplan and Meier. The probability of progression free survival at 6 months will be summarized. Response rates will be calculated as the percent of patients whose best response is a CR or PR, and the fraction of responses obtained will have a 95% confidence interval, which takes into consideration the two-stage nature of the design. Toxicity information recorded will include the type, severity, time of onset, time of resolution, and the probable association with the study regimen. Tables will be constructed to summarize the observed incidence by severity and type of toxicity.

**Time to progression** will be taken as the number of days from enrollment until: (1) disease progression; (2) death because of treatment complications; (3) resection of measurable tumor; or (4) last patient follow-up whichever is first. Patients will be considered to have experienced a progression event if (1) or (2) occurs. Otherwise, the patient will be considered censored for time to progression.

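### The bar on determining progression before an undefined Day 60 evaluation leaves the event status and date of progression on an earlier unscheduled scan contradictory

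*Combined protocol and SAP*

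**What the plan says.** All references are to the combined protocol and SAP.

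- **Section 6.5.1.1, target lesions.** Progression is a 20% and 5 mm increase in the sum of diameters. The same paragraph adds that "the appearance of one or more new lesions is also considered progressions", followed by the note that "determination of PD will not be made prior to the Day 60 evaluation".
- **Section 6.5.1.1, non-target lesions and best overall response table.** Any new lesion is progression. No day limit is attached.
- **Sections 6.5.6 and 6.5.8.** Both foresee progression or new lesions seen around cycle 2 and ask for a confirmatory scan at the next scheduled restaging. Section 6.5.6 then says: "If confirmed, progression should be dated by the initial time when the lesions are first detected". Section 6.5.8 has the same rule for bone lesions.
- **Section 3.1.** "Two weeks (plus 12 or minus 3 days) following each course of therapy (three 21-day cycles) patients will undergo appropriate staging studies". Section 3.5.2 repeats this timing. Neither section, nor Appendix 2, names a Day 60 visit.
- **Sections 3.4 and 3.6.2.** Patients continue mithramycin "for as long as they do not experience clinical or radiographic disease progression", and progressive disease is an off-study criterion. The Précis also removes progressing patients. None of these mentions Day 60.
- **Section 3.5.4.** Scans after treatment are for some patients only: "For patients with stable disease or responding to therapy, the following will be done every 2 months until off study criteria are met".
- **Section 8.1.** Time to progression runs from enrollment, in response-evaluable patients. "Patients will be considered to have experienced a progression event if (1) or (2) occurs", meaning disease progression or death from treatment complications. Everyone else is censored.
- **Section 8.2.** Response evaluability requires a full course, given there as 4 cycles and 28 doses. Elsewhere a course is three cycles.

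**The concern.** Take a patient whose unscheduled scan on Day 35 shows new lesions. The note in 6.5.1.1 says progression has not been determined. The non-target definition and the response table in the same section say it has. Section 3.4 ends treatment on radiographic progression. Section 6.5.6 would date the event to Day 35, but only if a later scheduled scan confirms it. If the patient is neither stable nor responding, 3.5.4 provides no further scans. Section 8.1 has no rule for the case.

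Whether this patient is an event, and on what date, is therefore left to whoever codes the data. At stake are the early part of the time-to-progression curve and, if such patients drop out of the analysis, the 6-month PFS estimate. The patients affected are those who do worst, so losing them would not be neutral.

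**Working it through.** **1. The plan's own figures.** The documents give no sample size, event count or expected median for time to progression or 6-month PFS. The only figures to reproduce are those of the two-stage design in Section 8 (0 of 7 stops; 3 or more of 21 is of interest; rates 5% and 30%). Early termination at 5% is 0.95^7 = 0.698, against the stated 70%. The exact two-stage binomial gives type I error 0.064 (limit 0.10) and power 0.904 (target 0.90). The design reproduces, and the note does not enter it.

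**2. When the first planned scan falls.** The inputs are 21-day cycles with dosing on days 1–7 (Section 3.2) and restaging 14 days after a course, +12/−3 (Section 3.1).

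- Last dose of cycle 3: 1 + 2×21 + 6 = Day 49. End of cycle 3: Day 63. End of cycle 2: Day 42.
- Counted from the last dose: target 49 + 14 = Day 63, window Day 60–75.
- Counted from the end of cycle 3: target 63 + 14 = Day 77, window Day 74–89.
- Corner case: Section 3.2 lets a cycle interval shorten by 3 days. If both are shortened, the last dose is 1 + 2×18 + 6 = Day 43, and the earliest scan counted from it is 43 + 11 = Day 54.

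So on the nominal schedule no planned scan precedes Day 60. The scans around cycle 2 that 6.5.6 and 6.5.8 contemplate (about Day 42) would precede it, but Section 3.5.2 schedules no tumor scan then.

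**3. What delay does, and what loss does.** The medians are assumptions. Take 21 patients (one full cohort) at exponential quantiles t_i = −ln(1 − (i − 0.5)/21)/λ, with λ = ln 2/median, and the Kaplan-Meier estimate at Day 183.

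| Assumed median (days) | Progress before Day 60 | Beyond Day 183 | Dated when they occur | Moved to Day 60 or Day 77 | All early progressors censored or excluded |
|---|---|---|---|---|---|
| 60 | 10 | 3 | 3/21 = 0.143 | 0.143 | 3/11 = 0.273 |
| 90 | 8 | 5 | 5/21 = 0.238 | 0.238 | 5/13 = 0.385 |
| 120 | 6 | 7 | 7/21 = 0.333 | 0.333 | 7/15 = 0.467 |
| 180 | 4 | 10 | 10/21 = 0.476 | 0.476 | 10/17 = 0.588 |

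Late dating flattens the curve before Day 60 or 77 and leaves the six-month value alone. Only loss of the patient raises it, by 11 to 15 points if every early progressor is lost.

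**4. Who is in the analysis set.** Section 8.1 restricts time to progression to response-evaluable patients, and 8.2 requires 28 doses. Dose 28 falls nominally on 1 + 3×21 + 6 = Day 70. With every interval shortened by 3 days it falls on 1 + 3×18 + 6 = Day 61. A patient who stops before Day 60 therefore cannot have 28 doses and is outside the set, whatever the note says. The Day 35 patient has had at most 14 doses.

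If a course is instead read as three cycles (21 doses, nominally Day 49), the exposed group is those who stop between Day 49 and Day 60. At assumed exponential medians of 3 and 2 months (91.3 and 60.9 days):

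- 0.5^(49/91.3) − 0.5^(60/91.3) = 5.5%
- 0.5^(49/60.9) − 0.5^(60/60.9) = 6.7%

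**The case against.** The case for leaving the text alone has real weight. The note sits under target lesions, and its natural meaning is that progression is not called before the first scheduled restaging, which nominally opens on Day 60. It postpones a determination; no section says that an early progression is censored or discarded. Sections 6.5.6 and 6.5.8 date confirmed progression back to first detection. Time to progression is not among the objectives in Section 1.1. It is a descriptive summary with no decision rule, in at most 21 patients per cohort.

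Most of this stands, and it limits the size of the problem. It does not settle the conflict. The natural reading is not the written one, and the note follows directly on the sentence about new lesions. Back-dating depends on confirmation at a later scheduled scan, which a patient already off treatment or off study may never have. Sections 6.5.6 and 6.5.8 also presuppose the early findings that the note refuses to call progression, so they contradict it rather than complete it.

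A reader might go further and infer that early progressions can never be counted, that these patients are all censored, and that 6-month PFS is inflated accordingly. For example, with a 3-month exponential median and 37% progressing before Day 60, a true 25% would be estimated at 28% to 39% when a quarter to all of them are censored. The documents do not support that. It keeps every early progressor in the Kaplan-Meier set, whereas 8.1 and 8.2 together exclude those who stop before Day 60. The fractions assumed censored also have no source in the documents.

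**Conclusion.** The concern holds as a conflict of rules. For RECIST progression documented on an unscheduled scan before Day 60, the plan gives contradictory answers on whether it is an event and on what date, so the event may be lost or dated late.

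Its effect on 6-month PFS is nil if the only consequence is delay and the patient stays in the analysis. The 11 to 15 points in the table bound the all-lost case under assumed exponential medians of 60 to 180 days. They are not an estimate of what the note does: under the 28-dose rule, patients who stop before Day 60 are excluded by 8.2 in any case. Correcting the note alone would therefore not bring early progressors into time to progression. The primary response endpoint's two-stage design figures are untouched. This is a modest point that is cheap to correct.

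**What to change.** 1. In 6.5.1.1, replace the undefined evaluation by an explicit reference to the first scheduled restaging of Sections 3.1 and 3.5.2, and say whether that is counted from the last dose or from the end of cycle 3.
2. In 8.1, state that, for the time-to-progression analysis, RECIST progression documented at any assessment, scheduled or not, is an event on the date first documented, consistent with the dating rule in 6.5.6 and 6.5.8.
3. Make the evaluability rule in 8.2 consistent with this, so that early progressors are not dropped from time to progression, for example by giving that analysis its own patient set. Reconcile the four-cycle course in 8.2 with the three-cycle course elsewhere.
4. Reconcile the note with the stopping and off-study language in 3.1, 3.4, 3.6.2 and the Précis. Progression also governs treatment, so the sponsor must settle this; no view is taken here on which stopping rule is right.

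The cost is a few sentences and no new scans. Early progression times will look slightly less favorable.
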